12.5 Planned Interim Analysis

Not applicable.

12.6 Exploratory Analysis

Cognitive and behavioral tasks

The outcomes of the cognitive and behavioral tasks (Cue Reactivity (CR), Card Guessing Task (CGT), Delay Discounting task (DD), Balloon Analog Risk Task (BART), and Stop Signal Reaction Time task (SSRT)) are collected at baseline and at the 6-, and 12-month time points. These outcome measures include:

- craving, positive affect, negative affect, calm, and excitement scores for CR
- β - and γ -spectral power for CGT
- discounting rate (k) for DD
- adjusted pumps for BART
- SSRT

H5: LP DBS will normalize reward processing (reduce baseline and increase event-related spectral power in the β - and γ -range) and reduce alcohol CR, temporal discounting, risk taking, and motor impulsivity post-DBS compared to baseline.

Analysis of H5: The outcome measures will be analyzed like the PET measure of target engagement measures, using one-way RM ANOVA between baseline values, DBS-ON at 6 months, and DBS-ON at 12 months, with post-hoc comparisons to the baseline.

Intra-operative neurophysiology

H6. Different neuronal populations in the LP encode rewarding vs. aversive stimuli and these neurons respond differently for alcohol vs. neutral cues.

H6.1: a population of LP neurons will show significant increase in neuronal firing during reward expectation.

H6.2: a different population of LP neurons will show significant increase in responding during loss expectation.

Analysis of H6.1 and H6.2: A 2-way repeated-measure ANOVA will be used to compare the firing frequency of the different epochs (first epoch represents baseline firing) in different trial types (win vs. neutral vs. loss) (dependent variable = firing rate, factor 1 = epoch, factor 2 = trial type), with post-hoc comparisons. In task responsive neurons, we expect to see significant epoch X trial type interaction, as well as significant effect of epochs and trial types.

13 Data and Safety Monitoring

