 - 2) Card Guessing Task (CGT).** This task measures reward processing. The CGT consists of up to 240 trials (3-trial types; ~23 min) coded in Neurobehavioral Systems Presentation. Trials occur in the setting of alcohol vs. neutral cues. Subjects are asked to press one of two buttons indicating whether a card will show a low (1-4) or high (6-9) number. EEG will be recorded during the CGT.
 - 3) Balloon Analog Risk Task (BART).** This task measures propensity for risk taking. A total of up to 350 trials will be performed. Trials will occur in the setting of either an alcohol-related or a neutral cue, followed by an image of a deflated red balloon. The participant will then press a button to increase the size of the balloon. With each pump after the first, the probability of balloon pop increases.
 - 4) Delay Discounting (DD).** The DD task measures decisional impulsivity. This task consists of two 15-minute runs, each of which comprises up to 150 trials. In each trial, a picture cue (either alcohol-related or neutral) is then shown. Each trial presents the participant with a choice between an immediate small reward or delayed larger reward.

5) Stop Signal Reaction Time Task (SSRT). The SSRT task consists of 3 x 10-minute blocks, each with up to 128 trials (~30 min for the 3 blocks). Participants must respond when shown a black square (Go Signal) but then must withhold their response if the color of the square changes to red. This task measures motor impulsivity and behavioral control.

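### H6 predicts different responses to alcohol and neutral cues, but its only planned ANOVA has no cue factor, so that clause has no specified test

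*Protocol*

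**What the plan says.** Protocol section 12.6, under intra-operative neurophysiology, gives H6 two parts; SAP section 12.6 has the same text. The first part is that separate populations of limbic pallidum (LP) neurons encode rewarding and aversive stimuli. The second is that "these neurons respond differently for alcohol vs. neutral cues".

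Two sub-hypotheses follow. H6.1 is that "a population of LP neurons will show significant increase in neuronal firing during reward expectation". H6.2 is that "a different population of LP neurons will show significant increase in responding during loss expectation". Neither mentions cue.

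One analysis is given: "Analysis of H6.1 and H6.2: A 2-way repeated-measure ANOVA will be used to compare the firing frequency of the different epochs". Its terms are listed as "dependent variable = firing rate, factor 1 = epoch, factor 2 = trial type". Trial type has the levels win, neutral and loss, so neutral here is a kind of trial and not the neutral cue. Post-hoc comparisons are mentioned but not named. The plan then states an expectation: "In task responsive neurons, we expect to see significant epoch X trial type interaction, as well as significant effect of epochs and trial types".

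On the task itself, Protocol section 7.4 says of the Card Guessing Task: "Trials occur in the setting of alcohol vs. neutral cues". It gives up to 240 trials of 3 trial types. The schedule in Appendix A lists this task with the intra-operative physiology.

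**The concern.** The cue clause is the only alcohol-specific part of H6. It links the recordings to alcohol use disorder rather than to reward and loss in general. The task collects the contrast, but the listed model averages over it. If cue tests are added only after the data have been seen, they will carry less weight than tests named now, and the recordings are made during brain surgery that would not be repeated for research.

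There is a second, smaller gap. H6.1 and H6.2 each speak of a population of neurons with a significant increase. The plan gives no significance level, multiplicity rule, number of neurons, or minimum number or share of responsive neurons. If each neuron is tested separately, some will be significant by chance, and nothing in the plan says how many would be too few to count as a population.

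**Working it through.** The documents give no power, significance level or neuron count for H6, so there is no planned figure to reproduce.

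**1. Hypotheses against tests**

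| Claim in section 12.6 | Term in the planned ANOVA |
|---|---|
| H6.1, firing rises in reward expectation | epoch, trial type, epoch x trial type |
| H6.2, firing rises in loss expectation | the same terms |
| H6, response differs by alcohol or neutral cue | none |

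Post-hoc comparisons in this model compare levels of epoch and trial type, so they do not supply a cue contrast. The extra covariates offered in section 12.1 are socio-demographic.

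**2. What the two-factor model does with a cue effect**

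Suppose that in one epoch alcohol cues shift firing by +d and neutral cues by -d, with equal numbers of each in every trial type. Each epoch-by-type cell mean then shifts by (+d - d)/2 = 0. The effect leaves all the cell means and goes into the error term. If only alcohol cues shift firing, by d, every trial type shifts by d/2 in that epoch. The model then shows an epoch effect and cannot attribute it to cue.

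A simulation agrees. It assumed 3 trial types x 80 trials x 4 epochs, normal errors, a cue effect of +/-0.5 SD in one epoch, and 10,000 runs. Rejection rates at 5% were 4.5% (trial type), 3.9% (epoch) and 3.7% (interaction). None exceeds the nominal level.

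**3. Trials per cell with cue added**

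240 / (3 trial types x 2 cues) = 40, against 240 / 3 = 80 now. This assumes that all 240 trials are run and are balanced. No separate intra-operative trial count is given.

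**4. Chance findings**

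The assumptions are one ANOVA per neuron, 5% per test, independent neurons and no true responders. The neuron count N is also assumed. P(at least one) = 1 - (1 - a)^N, where a is the chance rate per neuron.

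| N | one undirected test, a = 0.05 | predicted direction, a = 0.025 | all three effects, full null, a = 0.05^3 = 0.000125 |
|---|---|---|---|
| 20 | 64% | 40% | 0.2% |
| 50 | 92% | 72% | 0.6% |
| 100 | 99% | 92% | 1.2% |

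- The expected number of false responders in the first column is 0.05N, which is 1, 2.5 and 5.
- Both populations appearing by chance, at a = 0.025 for each direction, has probability 1 - 2(1 - a)^N + (1 - 2a)^N. This is 15%, 51% and 85% for N = 20, 50 and 100.
- If neurons have a real epoch effect that is unrelated to trial type, the three-effect rule has a of about 0.05^2 = 0.0025. That gives 7% for 30 neurons and 22% for 100.
- Simulated rates per neuron for the three-effect rule were 0.0001 (full null) and 0.0032 (real epoch effect), close to these products.

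**The case against.** The strongest reply is that H6 is exploratory. Intra-operative neurophysiology is not among the objectives or endpoints in section 3, and it does not enter the safety and feasibility criteria in section 12.3. That stands, and it limits the weight of the point. It does not supply the missing cue analysis.

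A reader might infer that H6.1 and H6.2 can hardly fail. The documents do not support this, for three reasons.

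- Testing neuron by neuron is only suggested, by the reference to task-responsive neurons. It is not stated. If neurons are pooled in one model, the per-neuron figures do not apply.
- The hypotheses are directional, and H6.2 needs a second, different population. Both appear by chance in 15% of cases with 20 neurons, which is far from certain.
- The plan names a demanding pattern, an interaction plus both main effects. If that were binding, chance passes would be rare. It is worded as an expectation, so the gap remains, but the 64% to 99% range is the least favourable reading.

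Nor is it a fault of H6 that the neurons come from three people. That is the stated pilot size. Reporting by participant is still useful, because all responsive neurons could come from one person.

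**Conclusion.** The main point holds and follows from the text without assumptions: the cue clause of H6 has no specified test. That a balanced cue effect would be missed follows from the algebra, and the simulation shows it under its stated settings.

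The secondary point is conditional. With per-neuron testing at 5%, independence and 20 to 100 neurons, the probability of at least one false responder runs from 64% to 99% on a single undirected test. It is 40% to 92% in the predicted direction, and about 1% or less if all three effects are required under the full null. The plan does not say which rule applies. That is a reason to define a responsive neuron, and not a reason to call the hypotheses untestable. Neither point touches the safety or feasibility conclusions.

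**What to change.** In section 12.6 of both documents:

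1. Add cue (alcohol vs neutral) as a third within-neuron factor for H6. Name two tests, cue x epoch and cue x epoch x trial type. Both are needed, because a cue difference that is the same for win, neutral and loss trials shows in cue x epoch and not in the three-way term.
2. State whether the ANOVA is run for each neuron. If so, define a responsive neuron by one of these rules: require the interaction and both main effects; control the false discovery rate across neurons; or compare the number of responsive neurons with the chance number. On a binomial test against 5%, the last rule needs at least 4 of 20 (P = 0.016), 5 of 30 (P = 0.016), 6 of 50 (P = 0.038) or 10 of 100 (P = 0.028). The three-effect rule protects less well if a non-specific epoch effect is real, as shown above.
3. Report the number of neurons recorded and the number responsive for each participant.

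The cost is a few lines of text and extra model terms, with no new procedure or data. Cells become smaller, at most about 40 trials per cue-by-type combination under the balance assumption, so the three-way test will be less precise than the present two-way one.

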13.1 Data Safety Monitoring Plan

Monitoring of subject safety and data quality will be the responsibility of all study personnel on the project, with primary responsibility and supervision by the principal investigators.

There will be an evaluation of the progress of the research study, including assessments of data quality, timelines, participant recruitment, accrual, and retention. The Investigator will also review the outcome and adverse effect data to determine whether there is any change to the anticipated benefit-to-risk ratio of study participation and whether the study should continue as originally designed or should it be re-evaluated and changed. A summary report of data and safety monitoring meetings will be provided to the IRB at the time of the continuing review.

To protect confidentiality of patient information we will use established procedures such as storing data in locked cabinets within locked offices or locked data rooms. Report forms are de-identified to avoid revealing the identity of participants. Data analyses will be performed using the research codes as identifiers. All data will be encrypted prior to any electronic transfer. Electronic records will be kept in computer files that are password-protected and housed on the UPMC network behind the UPMC firewall. The key linking names and study identification numbers will be kept at the study site but separately from the data sets with limited access by study personnel. Only study personnel will have access to the data sets on protected servers.

Primary data management will be performed by MPIs and study staff. The Department of Psychiatry's Office of Academic Computing (OAC) will assist in data management for this proposal. The OAC comprises staff (system administrator, computer operators and programmers) and services (printer, file and database servers). The OAC provides a client/server environment for data entry and management, data processing, statistical and graphical analysis, electronic mail, and word processing. Demographic, psychiatric, biological, behavioral, and psychosocial assessment data can be entered via automated forms processed on a PC and stored in a SQL Server relational database management system on a database server computer (e.g., web-based questionnaires (WebDataXpress). Facilities include LINUX systems for time series, genetic and brain imaging data processing, management, and analysis, Microsoft SQL Server databases, servers and workstations dedicated to data collection.

File servers and workstations are behind a firewall, restricting access initiated from the outside. The Intranet server can be accessed from outside the firewall only by using Transport Layer Security and full UPMC account authentication and authorization. The database server and file servers are NOT accessible from outside of the firewall. Using the proxy server greatly reduces the possibility that an intruder can gain direct access to the web server. The only traffic permitted to the server will be via the 128-bit encryption SSL (Secure Socket Layer) protocol.

No local accounts are used and all access to files and databases is restricted. Login procedures for data entry and access are restricted to designated users through database software protection. The authorized service accounts have "insert-only" permissions to the database. Only select members of the study team have access to the specific folders that contain de-identified data.

All data will be kept for a minimum of 7 years after completion of the project.

13.2 Parameters to be Monitored

The following progress will be monitored throughout the course of the research to ensure the safety of subjects as well as the integrity and confidentiality of their data.

- An evaluation of the progress of the research study, including subject recruitment and retention, and an assessment of the timeliness and quality of the data.
- A review of collected data (including adverse effects, unanticipated problems requiring reporting and those captured on the non-compliance log, and subject withdrawals) to determine whether there is a change to the anticipated benefit-to-risk assessment of study participation and whether the study should continue as originally designed, should be changed, or should be terminated.
- An assessment of external factors or relevant information (e.g. pertinent scientific literature reports or therapeutic development, results of related studies) that may have an impact on the safety and study participants or the ethics of the research study.
- A review of study procedures designed to protect the privacy of the research subjects and the confidentiality of their research data.

13.3 Frequency of Monitoring

The study team will review subject safety data as it is reported and documented. The study team will meet on a monthly basis to review subject recruitment, data, source documentation and identification of adverse events, complaints and confidentiality of subjects.

13.4 Clinical Monitoring

In accordance with 21 CFR 312.50 clinical site monitoring will be conducted to ensure that the rights and well-being of trial participants are protected, that the reported trial data are accurate, complete, and that the conduct of the trial follows currently approved protocol.

Post-operative clinical site monitoring: after DBS implantation, participants will receive a post-operative CT scan to assess DBS electrodes placement and to screen for the presence of intracranial hemorrhage. Participants will also be clinically monitored overnight in the neurocritical care unit. While in the intensive care unit, participants will have routine assessments by clinical staff to screen for any signs or symptoms of 1) focal neurologic deficits (e.g., weakness, sensory loss, vision problems), 2) mental status changes, 3) increased intracranial pressure (e.g., headaches, somnolence), and 4) infection of the wound, brain, or meninges.

Clinical monitoring during follow-up visits: Participants are clinically assessed during follow-up visits to determine whether DBS surgery or stimulation, or any other study intervention (PET scan, etc...) has resulted in any adverse effects (medical, neurologic, neurosurgical, psychiatric, or other). In addition, to evaluate whether DBS manipulations adversely affect cognitive functions, neuropsychological testing is performed at baseline and after 6 months of DBS stimulation, and then at 12 months. If DBS-related side

effects related to stimulation parameters are observed, the DBS parameters will be changed. During the blinded portions of the study, adverse effects assessments will be made based on the assumption that the stimulation is ON.

If an adverse effect is deemed serious and potentially linked to the study, the blind may be broken, the device can be turned off, or the parameters can be changed.

All adverse effects will be followed by the study team until resolved or back to baseline state.

Adverse effects that are not responsive to changes in stimulation parameters will be brought to the attention of the DSMB to determine if the device should be removed and if the participant should be withdrawn from the study.

The participants will be asked to identify a family member or a friend who can contact the study team on their behalf if needed for safety concerns.

Finally, a nurse with physician back-up will be available 24 hours per day to answer their questions and address potential concerns.

13.5 Data and Safety Monitoring Board

Since the protocol used in this proposal is classified as “Greater than minimal risk”, an independent Data and Safety Monitoring Board (DSMB) will be created to review and oversee this study. The first meeting of the DSMB will take place before initiation of the study to discuss the protocol, approve the study commencement, and establish guidelines to monitor the study. Follow-up meeting frequency will be determined during the first meeting, and an emergency meeting will be called at any time by the Chairperson, should questions of patient safety arise. After initial approval and at periodic intervals (to be determined by the DSMB committee) during the study, the DSMB responsibilities are to:

1. Review the research protocol, informed consent documents, and plans for data and safety monitoring
2. Evaluate the progress of the study, including periodic assessments of data quality and timeliness, participant recruitment, accrual and retention, participant risk versus benefit, adverse events, patient withdrawals, unanticipated problems, performance of the trial site, and other factors that can affect the study outcome
3. Review safety data after the 3 participants have completed 6-months post-DBS assessments, and determine if the study met safety milestones (if the adverse events are not of a higher grade or incidence than expected)
4. Consider factors external to the study when relevant information becomes available, such as scientific or therapeutic developments that may have an impact on the safety of the participants or the ethics of the study
5. Review clinical center performance, make recommendations and assist in the resolution of problems reported by the study team
6. Protect the safety of the study participants
7. Report on the safety and progress of the study
8. Make recommendations to the study team, and if required, to the NIH/NIAAA concerning continuation, termination or other modifications of the study based on the observed beneficial or adverse effects of the study intervention
9. Monitor the confidentiality of the study data and the results of monitoring

10. Assist the study team by commenting on any problems with study conduct, enrollment, sample size and/or data collection
11. Each serious adverse effect will prompt a review by the DSMB, and the study will be suspended until it is determined whether the SAE is study-related or unrelated

The DSMB will include individuals with expertise in *Neurology, Psychiatry, Neurosurgery, Alcohol Use Disorder, DBS, Bioethics and Clinical Trials/Biostatistics*. Members will consist of persons independent of the investigators who have no financial, scientific, or other conflict of interest with the study. Written documentation attesting to absence of conflict of interest will be required.

The University of Pittsburgh Office of Clinical Research, Health Sciences / CTSI will provide the logistical management and support of the DSMB. A safety officer (chairperson) will be identified at the first meeting. This person will be the contact person for serious AE reporting. Procedures for this will be discussed at the first meeting.

14 Regulatory, Ethical, and Study Oversight

14.1 IRB Approval

The Investigator will obtain, from the University of Pittsburgh IRB, prospective approval of the clinical protocol and corresponding informed consent form(s); modifications to the clinical protocol and corresponding informed consent forms, and advertisements (i.e., directed at potential research subjects) for study recruitment.

The only circumstance in which a deviation from the current IRB-approved clinical protocol/consent form(s) may be initiated in the absence of prospective IRB approval is to eliminate an apparent immediate hazard to the research subject(s). In such circumstances, the Investigator will promptly notify the University of Pittsburgh IRB of the deviation. The Investigator should also notify the sponsor of this event.

The IRB will review and approve the Informed Consent Document for the study and provide institutional oversight of data and safety issues. The study protocol will be approved prior to recruiting or obtaining consent from any participants. Moreover, the study will be reviewed at a minimum of annual basis (or more frequently as deemed necessary) by the IRB committee. Each participant will sign the approved Informed Consent Form prior to participating in the study.

The University of Pittsburgh IRB operates in compliance with FDA regulations at 21 CFR Parts 50 and 21 CFR 56, and in conformance with applicable ICH Guidelines on GCP.

14.2 Informed Consent Procedures

Consent will be obtained prior to screening. The study coordinator will review the written informed consent form with the potential participant. A physician investigator will answer any questions and ensure the participant understands the study rationale, procedures, and the potential risks and benefits, all of which are included in the IRB-approved consent form, and the potential participant will decide whether to then sign the consent form. If the participant requires more time to decide about their participation in the study, then signing of the consent can be postponed to a later date, and the participant can review a copy of the consent in the meantime. Once signed, the original consent form will be stored under double lock and a copy will be given to the participant.

Participants must be able to consent for themselves in order to participate. Cognitive capacity and competency will be evaluated during the initial neuropsychological evaluation, and participants who are determined to lack full capacity to consent will be excluded.

Participants will be informed after the conclusion of all study procedures.

